2.7.3 Other Safety Data

The FAS will be used for summaries and listings of other safety data discussed in this section except for the second formal interim analysis for Cohort 1 after Amendment 3 where the Interim

Analysis Set 2 for Cohort 1 will be used. In general, summaries will be provided only for the on-treatment safety assessments, which are the assessments occurring or taken during the on-treatment period.

2.7.3.1 *Ophthalmologic Assessment*

Both visual acuity score (logMAR) and tonometry will be summarized at baseline, each post-baseline visit (based on the visit schedule defined in the protocol along with a window), the maximum and minimum observed post-baseline values, and last observed value, along with the change from baseline.

Along with the summary described above, the number (percentage) of clinically significant changes in visual acuity score (logMAR) will be also summarized:

- <0.1 logMAR
- 0.1 - <0.2 logMAR
- 0.2 - <0.3 logMAR
- ≥ 0.3 logMAR

In addition, the number (percentage) of clinically significant values in tonometry will be summarized by visit:

- ≤ 21 mmHg
- > 21 mmHg

Number (%) of clinically significant abnormalities will also be summarized by visit for slit lamp, OCT, and fundoscopy exams.

2.7.3.2 *Left Ventricular Ejection Fraction*

Left ventricular ejection fraction (LVEF) will be summarized for baseline, each post-baseline visit (based on the scheduled defined in the protocol along with a window), minimum post-baseline, along with the changes from baseline. Shift tables of the minimum post-baseline LVEF ($<40\%$, 40% to 50% , $\geq 50\%$) with baseline LVEF status ($\geq 50\%$, $<50\%$) will be provided.

Clinically significant changes of LVEF defined below will also be presented:

1. Absolute decrease from baseline $>10\%$ but $<20\%$ and LVEF $\geq 40\%$ to $<50\%$
2. Absolute decrease from baseline $\geq 20\%$ and LVEF $\geq 20\%$ to $<40\%$

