  - Continuous or intermittent small molecule therapeutics within a period of time that is  $\leq 5$  t1/2 or  $\leq 4$  weeks (whichever is shorter) prior to starting study drug
  - Any other investigational agents within a period of time that is  $\leq 5$  t1/2 or less than the cycle length used for that treatment or  $\leq 4$  weeks (whichever is shortest) prior to starting study drug
  - Wide field radiotherapy (including therapeutic radioisotopes such as strontium 89) ≤ 4 weeks or limited field radiation for palliation ≤ 2 weeks prior to starting study drug
- 10. Patients who are currently receiving, or are planning to receive during participation in this study, treatment with agents that are known strong inducers or inhibitors of CYP3A4 and medications which increase serum phosphorus and/or calcium concentration are excluded. (Refer to Appendix 2 for list of prohibited medications). Patients are not permitted to receive enzyme-inducing anti-epileptic drugs
- 11. Consumption of grapefruit, grapefruit juice, grapefruit hybrids, pomegranates, star fruits, pomelos, Seville oranges, or products containing juice of these fruits, within 7 days prior to first dose
- 12. Insufficient bone marrow function
  - ANC  $< 1,000/\text{mm}^3 [1.0 \times 10^9/\text{L}]$
  - Platelets  $< 75,000/\text{mm}^3 [75 \times 10^9/\text{L}]$
  - Hemoglobin < 9.0 g/dL
- 13. Insufficient hepatic and renal function

- Total bilirubin > 1.5x ULN (for patients with documented Gilbert syndrome, direct bilirubin ≤1.5x ULN and enrollment requires approval by the medical monitor)
- AST/SGOT and ALT/SGPT > 2.5x ULN (AST and ALT > 5x ULN in the presence of liver metastases)
- Serum creatinine > 1.5x ULN and a calculated (using the Cockcroft-Gault formula [Cockcroft 1976]) or measured creatinine clearance of < 45 mL/min
- 14. Abnormal calcium or phosphorus:
  - Inorganic phosphorus outside of normal limits
  - Total serum calcium (can be corrected) outside of normal limits
  - Calcium-phosphorus product ≥55 mg²/dL²
- 15. Clinically significant cardiac disease including any of the following:
  - Congestive heart failure requiring treatment (NYHA Grade ≥ 2), LVEF < 50% as determined by MUGA scan or ECHO, or uncontrolled hypertension (refer to WHOISH guidelines)
  - History or presence of clinically significant ventricular arrhythmias, atrial fibrillation, resting bradycardia, or conduction abnormality

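### The three LVEF categories in SAP 2.7.3.2 leave two combinations of fall and level uncounted, so the table of clinically significant changes is not ordered by severity

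*SAP*

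**What the plan says.** SAP 2.7.3.2 (Left Ventricular Ejection Fraction) plans three kinds of output.

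- LVEF is summarised at baseline, at each post-baseline visit and at the post-baseline minimum, with changes from baseline.
- "Shift tables of the minimum post-baseline LVEF" are planned, in bands of below 40%, 40% to 50%, and 50% or more, against a baseline of 50% or more or below 50%.
- A display of changes labelled clinically significant is introduced by "Clinically significant changes of LVEF defined below will also be presented".

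The third output has three categories. The first reads "Absolute decrease from baseline $>10\%$ but $<20\%$ and LVEF $\geq 40\%$ to $<50" per cent. The second reads "Absolute decrease from baseline $\geq 20\%$ and LVEF $\geq 20\%$ to $<40" per cent. The third is an LVEF below 20%, with no condition on the fall.

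Protocol 5.3, exclusion criterion 15, excludes patients with "LVEF < 50% as determined by MUGA scan or ECHO". An eligible patient therefore starts at 50% or above.

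**The concern.** Categories 1 and 2 each join a size of fall to an absolute level. Two bands of fall and two bands of level make four combinations, but the SAP defines only two of them. A patient whose fall lies in one band and whose level lies in the other is counted nowhere, even when the outcome is worse than one that is counted.

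LVEF is a planned cardiac safety assessment in this trial, and this table is the only LVEF output that combines size of fall with level in a patient count. A reader will take its total as the number of patients with an important decline. Under the present wording that total can omit larger declines while including smaller ones.

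**Working it through.** **Inputs.** The three categories and the shift-table bands come from SAP 2.7.3.2. The baseline limit of 50% comes from Protocol 5.3. The plan gives no figure of its own to reproduce.

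**Notation.** B is baseline LVEF, L is the lowest post-baseline LVEF, and D = B − L is the fall in percentage points. The SAP does not say whether the categories apply to the lowest value or to each visit. The lowest value is assumed here.

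**The rule as written, for D above 10 and L from 20% to below 50%:**

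| | L 40 to <50 | L 20 to <40 |
|---|---|---|
| D >10 to <20 | category 1 | none: gap (a) |
| D ≥20 | none: gap (b) | category 2 |

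**Two examples, both with eligible baselines:**

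- 52% to 35%: D = 52 − 35 = 17. Category 1 fails because 35 is below 40. Category 2 fails because 17 is below 20. Category 3 fails because 35 is not below 20.
- 65% to 42%: D = 65 − 42 = 23. Category 1 fails because 23 is not below 20. Category 2 fails because 42 is not below 40. Category 3 fails because 42 is not below 20.

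**Where the gaps lie.** Gap (a) needs L > B − 20 and L < 40, so it exists for B from 50 to below 60. Gap (b) needs L ≤ B − 20 with L from 40 to below 50, so it exists for B of 60 or more. Every eligible baseline therefore has one gap or the other.

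**Order of severity, whole-number values:**

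| Baseline | Category 1 | Counted nowhere | Category 2 |
|---|---|---|---|
| 50 | none | 31–39 | 20–30 |
| 52 | 40–41 | 33–39 | 20–32 |
| 55 | 40–44 | 36–39 | 20–35 |
| 65 | 46–49 | 40–45 | 20–39 |
| 70 | none | 40–49 | 20–39 |

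For one patient starting at 52%, a worsening lowest value moves from counted (41%) to not counted (39% to 33%) and back to counted (32%).

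**Shift-table bands.** The band from 40% to 50% and the band of 50% or more both contain exactly 50%, so a minimum of 50% has two possible cells.

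**The case against.** The strongest reply is that nothing is lost from LVEF reporting as a whole. The categories are an additional display. The same section summarises the minimum and the change from baseline. Protocol 10.5.2.4 has LVEF listed with notable values flagged. Protocol 7.2.2.7 requires significant new cardiac imaging findings, from the start of study drug to 30 days after its permanent discontinuation, to be recorded as adverse events, and SAP 5.2 searches for cardiac failure terms separately. No endpoint or decision rule depends on the three categories. This all stands, and it limits the finding to one table.

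A reader might infer that the shift table misses gap (b). It does not: 65% to 42% appears as a move from 50% or more to the 40% to 50% band, and 52% to 35% as a move to below 40%. What the shift table lacks is the size of the fall, so 65% to 42% looks the same as 51% to 49%.

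A reader might also turn the gaps into a percentage of missed cases. The documents do not allow that. Among whole-number pairs with a lowest value of 40% to 49% and a fall above 10 points, the uncounted share is 115 of 205 (56%) if baselines run from 50% to 75%, 65 of 155 (42%) if they stop at 70%, and 21 of 105 (20%) if they stop at 65%. These are shares of number pairs under an assumed range, not of patients.

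Reading the fall as relative does not rescue the rule. The SAP says absolute. On a relative reading, 52% to 35% (17/52 = 33%) would enter category 2, but 65% to 42% (23/65 = 35%) would still be in none.

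**Conclusion.** The definition is wrong as written. Two of the four combinations of fall and level are unassigned, at least one gap applies to every eligible baseline, and the resulting count is not ordered by severity. This follows from the SAP's wording alone and needs no assumption about the data, except that a patient is classified by the lowest value. If the rule were applied visit by visit, some patients might still be counted through a milder reading, but the worse reading would remain unclassified.

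The consequence is limited. The count in this one table can be too low; the other LVEF and adverse event outputs still include these patients. The number affected cannot be estimated and may be small. The documents do not support saying that patients disappear from safety reporting, or that any trial decision is affected.

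**What to change.** Keep the SAP's own thresholds, close the two gaps, and count each patient once in the worst category reached:

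1. LVEF 40% to below 50%, with an absolute fall of more than 10 and less than 20 points.
2. LVEF 20% to below 40% with a fall of more than 10 points, or LVEF 40% to below 50% with a fall of at least 20 points.
3. LVEF below 20%.

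Every fall of more than 10 points to below 50% then has exactly one category. From a baseline of 52%, values of 40–41% are category 1 and 20–39% category 2. From 65%, values of 46–49% are category 1 and 20–45% category 2. As now, a fall that leaves LVEF at 50% or more is outside the table.

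Simply replacing the joining word with an alternative (fall or level) is not advised. A fall of at least 20 points would then qualify for category 2 at any level, so 75% to 55% would rank above 60% to 41%.

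Change the shift-table bands to below 40%, 40% to below 50%, and 50% or more.

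The cost is an SAP wording change and minor table reprogramming. No new data are needed. The reported incidence may rise slightly.

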3. LVEF $<20\%$

2.7.3.3 *ECG and Cardiac Imaging Data*

The ECG analysis will be performed on all subjects who have received at least one dose of infigratinib with the baseline and at least one on-treatment post-baseline ECG assessment.

The average of the ECG parameters at each assessment should be used in the analyses. 12-lead ECGs including PR, QRS, QT, QTcF, QTcB, and HR intervals will be obtained central/local for each subject during the study. ECG data will be read and interpreted centrally. The ECG summaries will include all assessments available for the ECG parameter collected no later than 30 days after the last study treatment administration date.

ECG parameters will be summarized at baseline, each post-baseline visit (based on the nominal visit as collected from eCRF), the maximum and minimum observed post-baseline values, and last observed value, along with the change from baseline. For the maximum/minimum/last observed value, both scheduled and unscheduled assessments will be considered.

The number and percentage of subjects with notable ECG values will be presented.

- QT
 - New value of >500 ms
- QT, or QTcF
 - New value of >450 ms
 - New value of >480 ms
 - New value of >500 ms
 - Increase from baseline of >30 ms to ≤60 ms
 - Increase from baseline of >60 ms
- HR
 - Increase from baseline >25% and to a value >100 bpm
 - Decrease from baseline >25% and to a value <50 bpm
- PR
 - Increase from baseline >25% and to a value >200 ms
- QRS
 - Increase from baseline >25% and to a value >100 ms

A listing of all ECG assessments will be produced and notable values will be flagged. In the listing, the on-treatment assessments will be flagged. In addition, a shift table baseline to worst on-treatment result for overall assessments will also be produced.

In addition to the ECG analysis in CSR, a separate report on cardiac safety evaluation including QTc/PK modeling will be provided, based on a separate cardiac safety analysis plan.

2.7.3.4 *Vital Signs and ECOG Performance Status*

ECOG performance status will be summarized at baseline, each post-baseline visit (based on the visit schedule defined in the protocol along with a window), and the last observed value.

Vital sign assessments are performed in order to characterize basic body function. The following parameters were collected: height (cm), weight (kg), body temperature (°C), pulse rate (beats per minute), systolic and diastolic blood pressure (mmHg).

Vital signs (except height) collected during on-treatment will also be summarized using the same approach as for ECOG. The number and percentage of subjects with notable vital sign values (high/low) will be presented.

Table 6: Criteria for Notable Vital Sign Values

| Vital sign (unit) | Notable high value | Notable low value |
|---------------------------------|---|--|
| Systolic blood pressure (mmHg) | ≥180 and increase from baseline of ≥20 | ≤90 and decrease from baseline of ≥20 |
| Diastolic blood pressure (mmHg) | ≥105 and increase from baseline of ≥15 | ≤50 and decrease from baseline of ≥15 |
| Pulse rate (bpm) | ≥100 and increase from baseline of >25% | ≤50 and decrease from baseline of >25% |
| Body temperature (°C) | ≥39.1 | -- |

2.7.3.5 *Supportive Analyses for Secondary Objectives*

Not applicable.

2.7.3.6 *Tolerability*

Tolerability of study drug will be assessed by summarizing the number of dose interruptions and dose reductions. Reasons for dose interruption and dose reductions will be listed by subject and summarized. Cumulative dose, dose intensity and relative dose intensity of infigratinib will be listed by subject and summarized. Categories for relative dose intensity of infigratinib will be specified as ≤0.5, >0.5 - ≤0.75, >0.75 - ≤0.9, >0.9 - ≤1.0, and >1.0. The number and proportion of subjects within each category will be presented.

2.7.4 *Pharmacokinetics*

Subjects treated with FMI I and some subjects treated with FMI III (sparse PK group) will have limited PK collected as indicated in Table 10 of [CSP Amendment 5](#). For these subjects, only trough and 2-hr or 4-hr plasma concentration data will be collected. No PK parameters can be calculated for these subjects, but the concentration data may be used in the population PK modeling.

A secondary objective of this study is to characterize the single and multiple doses PK of infigratinib FMI III and FMI IV formulations. Data as per Table 11 of [CSP Amendment 5](#) will be available for about 20 subjects treated with FMI III and for all subjects enrolled in either Cohort 2 or Cohort 3 and treated with FMI IV. For these subjects, PK parameters as listed in [Table 7](#), may be determined from PK profiles after the first dose on Day 1 of Cycle 1 and Day 15

of Cycle 1 after repeated daily dosing using non-compartmental method(s) of WinNonlin (Pharsight, Mountain View, CA).

The sections below on the PK analysis are intended to provide general principle for the PK analysis. Additional details of the analysis approaches will be provided in a separate PK analysis plan.

Table 7: Non-compartmental Pharmacokinetic Parameters

| Term | Definition |
|---------------------|--|
| C_{\max} | Maximum observed plasma concentration after drug administration [mass \times volume $^{-1}$] |
| C_{trough} | Measured concentration at the end of a dosing interval (taken directly before next administration) [mass \times volume $^{-1}$] |
| T_{\max} | Time to reach C_{\max} [time] |
| AUC_{0-24} | Area under the concentration-time curve from 0 to 24 hours [mass \times time \times volume $^{-1}$] |
| $T_{1/2}$ | Elimination half-life associated with the terminal slope (λ_z) of a semi-logarithmic concentration-time curve [time] |
| AUC_{inf} | Area under the concentration-time curve from 0 to infinity [mass \times time \times volume $^{-1}$] |
| CL/F | Apparent clearance [dose/AUC] |
| V_z/F | Apparent volume of distribution [dose/AUC \times λ_z] |
| R_{acc} | Accumulation ratio calculated as AUC_{0-24} of C1D15/ AUC_{0-24} of C1D1 and C_{\max} of C1D15/ C_{\max} of C1D1 |

2.7.4.1 *Data Handling Principles*

Only PK blood samples with the date and time and for which the last prior dose dates and times are adequately recorded will be included in the PK analyses. Missing concentration values will be reported as is in data listings. Missing values for any PK parameters or concentrations will not be imputed and will be treated as missing. Below the limit of quantitation (BLQ) values will be displayed in the listings as is. BLQ values will be treated as zero for the calculation of the geometric means and geometric CV%.

At the time of analysis, concentration data from subjects may be removed from the estimation of certain PK parameters depending on the number of available blood samples, concomitant medications, vomiting, etc. Specific time points might be removed from the analysis set if technical issues with the sample are reported (eg, sampling issues, missing information). These data points will be identified at the time of analysis

2.7.4.2 *Data Analysis Principles*

Exploratory PK analysis may be conducted based on preliminary data prior to data base lock, and nominal time and dose information may be used.

PK data generated from this study may be used in conjunction with PK data from other clinical studies for population PK and PK/PD assessment. These assessments will be reported separately. If possible, exploratory comparisons will be made to historical pharmacokinetic data. Available PK data from this study may be modeled using a population pharmacokinetic data analysis approach in order to characterize the population pharmacokinetics of infigratinib. Any population PK data generated will be reported separate from the CSR.

All analyses will refer to infigratinib and its metabolites. Infigratinib and its metabolites concentration vs time data will be reported.

Analysis will be done separately for the three formulations. In addition, analyses that require derived PK parameters will be applicable to subjects treated with FMI III and FMI IV who have provided PK parameters based on extensive PK sampling as indicated in Table 11 of [CSP Amendment 5](#).

2.7.4.3 *Analysis Sets*

Only PK blood samples with the date and time and for which the last prior dose dates and times are adequately recorded will be included in the PK analyses. Samples taken from patients who vomited within 4 hours of dosing will be excluded from the analysis. The PAS will be used.

2.7.4.4 *Basic Tables, Figures, and Listings*

The PK concentration and PK parameters (when available for subjects treated with FMI III or FMI IV), will be summarized and listed using relevant statistics by treatment, and study day. Descriptive statistics (mean, SD, CV%, geometric mean, geometric CV%, median, and range) will be presented. Median, minimum and maximum will be calculated based on collected samples. When a geometric mean is presented, it will be stated as such. Only median values and ranges will be presented for T_{max} .

Graphical plots of individual and mean plasma concentration-time data will be generated for infigratinib and its metabolites. This graphical presentation will be applicable to subjects who are treated with FMI III and have PK profile collected as per Table 11 of [CSP Amendment 5](#). Further graphical exploratory analysis will be carried out if deemed appropriate.

Median, minimum and maximum will be calculated based on collected samples. All analyses will refer to infigratinib and its metabolites. Infigratinib and its metabolites concentration vs time data will be reported. Exploratory PK analysis may be conducted based on preliminary data prior to data base lock and nominal time and dose information may be used.

2.8 **Exploratory Analyses**

The exploratory analyses described below will be conducted if there are sufficient data available.

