#### 1.2.1.2.1 Clinical pharmacokinetics

The pharmacokinetics (PK) of BGJ398 and active metabolites have been evaluated following single and repeat daily doses in the ongoing phase I study (CBGJ398X2101). At 5 and 10 mg/day, plasma concentrations were low and frequently below the lower limit of quantification. Plasma concentrations were consistently quantifiable starting at 20 mg/day.

Following a single dose, median  $T_{max}$  was approximately 3-4 hours. The mean AUC0-24 on Day 1 increased approximately 9 fold from 20 to 150 mg. The mean terminal elimination half-life on Day 1( $T_{1/2}$ ) was 3-7 hr. Despite the relatively short half-life on Day 1, accumulation was observed with daily dosing at doses  $\geq$  60 mg, likely due to auto-inhibition of CYP3A4 mediated clearance pathways. Mean accumulation ratio ( $R_{acc}$ ) ranged from 3 to 8 on Days 15 and 28. Since dose interruptions occurred frequently following continuous daily dosing of BGJ398, PK parameters on Day 28 should be viewed with caution. The interpatient variability was high for BGJ398.

Concentration data from active metabolites BHS697 (desethyl metabolite) and BQR917 (Noxide) was available across all cohorts. CQM157 (aniline metabolite) was analyzed in a few patients following Amendment 6 of the BGJ398X2101 clinical protocol. In most patients, BHS697 and BQR917 were measurable at levels of ~5-50%, and <15% of parent exposure, respectively. Mean exposures on Day 1 (N=8) for CQM157 relative to BGJ398 varied across patients (3% -300%). CQM157 (N=4) did not appear to accumulate on daily dosing, whereas accumulation was observed for BGJ398 and metabolites BHS697 and BQR917.

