Blood for PK (extensive PK group) f	D	7.2.3.1			X	X		X	X		X		X		Day 1 Cycles 4-6					

Study Period	Category	Protocol Section	Molecular Pre-	Screening a			Сус	cle 1		T	Cyo	cle 2	Сус	cle 3	Subsequent	cycles	End of study treatment EOT	30-day follow-up	Disease Progression follow-up every 8 weeks Follow-u	months after EOT)
Day of Cycle				-21 to	1	2	8	15	16	21	1	15	1	15	1	15	≤14 days of the decision to discontinue the treatment			
Survival follow-up	D	7.1.6																		X
Antineoplastic therapies since discontinuation of study treatment	D	7.1.4																X	X	
Disease progression follow-up	D	7.1.6																	X	

<sup>a Screening assessments are to be completed within 21 days prior to the first dose of treatment, except for the radiological tumor assessment, which can be performed within 28 days prior to the first dose, and the ophthalmic examination, which should be completed within 14 days prior to first treatment.

Sparse PK sample group (Table 10): C1D1,2,8,15,21; and C2-6 D1 and D15.

Extensive PK group (Table 11): C1D1,2,15,16; and C2-6 D1.

<sup>b Ophthalmic assessments for subsequent cycles (ie, after C3D1) are to be completed at C7D1 and every 4 months after that (ie, C11D1, C15D1, C19D1, etc).

<sup>c Study drug will be administered in the clinic on the following days (PK sampling days):

<sup>d If written documentation of FGFR2 gene fusion or translocation is determined by a pre-existing test or local laboratory, archival tumor tissue from the same biopsy sample used to determine eligibility (or a new tumor biopsy collected before BGJ398 treatment) should be submitted to the central laboratory for confirmation testing within 14 days after the first treatment. Refer to the Laboratory Manual for the sample requirements and processing instructions for central laboratory testing.

<sup>e Sample will not be collected if a fresh tumor sample has already been collected at baseline for the purpose of DNA sequencing.

The first 20 patients enrolled in Cohort 1 and treated with FMI III and all patients enrolled in either Cohort 2 or Cohort 3 and treated with FMI IV (amendment 4) will follow the extensive PK sampling schedule.

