#### 10.5.3.1 Data handling principles

All concentrations below the lower limit of quantification (LLOQ) or missing data will be labeled as such in the concentration data listings. Concentrations below the LLOQ will be treated as zero in summary statistics.

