### 10.5.3.2.2 Basic tables, Figures and Listings

The PK concentration and PK (when available for patients treated with FMI III or FMI IV), will be summarized and listed using relevant statistics by formulation, and study day. Descriptive statistics (mean, SD, CV% or median [range]) will be presented. When a geometric mean is presented, it will be stated as such. Only median values and ranges will be presented for  $T_{\text{max}}$ .

Graphical plots of individual and mean plasma concentration-time data will be generated for BGJ398 and its metabolites. This graphical presentation will be applicable to patients who are treated with FMI III or FMI IV and have PK profile collected as per Table 11.

Median, minimum and maximum will be calculated based on collected samples. All analyses will refer to BGJ398 and its metabolites. BGJ398 and its metabolites concentration vs time data will be reported. Exploratory PK analysis may be conducted based on preliminary data prior to data base lock and nominal time and dose information may be used.

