4 CHANGE TO PROTOCOL SPECIFIED ANALYSES

None.

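### The SAP sets BLQ values to zero for geometric means and geometric CV%, which makes both statistics unusable in any concentration or trough cell that contains a BLQ value

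*SAP*

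**What the plan says.** SAP 2.7.4.1 (Data Handling Principles, pharmacokinetics) gives a rule for exactly two statistics: "BLQ values will be treated as zero for the calculation of the geometric means and geometric CV"%. SAP 2.7.4.4 then commits to reporting them for concentrations and PK parameters, by treatment and study day: "Descriptive statistics (mean, SD, CV%, geometric mean, geometric CV%, median, and range) will be presented". The scope includes metabolites: "All analyses will refer to infigratinib and its metabolites".

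The protocol also uses zero. Section 7.2.3.2 has concentrations under the LLOQ, about 1.0 ng/mL, reported as 0 ng/mL. Section 10.5.3.1 carries this into the analysis without separating arithmetic from geometric statistics: "Concentrations below the LLOQ will be treated as zero in summary statistics". Section 10.5.3.2.2 allows for geometric means: "When a geometric mean is presented, it will be stated as such".

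Neither document drops zeros before taking logs, substitutes a positive value, or says what to print when a cell contains a zero. The SAP describes its PK sections as general principle and leaves further detail to a separate PK analysis plan, which is not among the documents.

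**The concern.** Geometric statistics are computed on the log scale, and zero has no logarithm. The SAP therefore names the zero rule for the only two planned summaries in which it cannot work.

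The practical risk is what happens when the tables are programmed. Followed literally, an affected cell shows a geometric mean of 0 and no geometric CV%. Software may instead return missing, or drop the zeros without notice. The second outcome is an undocumented exclusion that moves the geometric mean up and the CV down. Characterising the PK of FMI III and FMI IV is a secondary objective, and Cycle 1 PK under FMI IV is to be compared with FMI III, so the handling should be fixed before the data are seen.

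**Working it through.** **1. The rule applied directly.** The formulas are GM = exp(mean of ln x), or equivalently (product of x)^(1/n), and geometric CV% = 100 × √(exp(variance of ln x) − 1). One zero makes the product 0, so GM = 0. The variance of ln x does not exist, so neither does the geometric CV%.

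Example with assumed values: n = 20, lognormal quantiles with GM 50 ng/mL and nominal CV 80%, lowest value replaced by 0.

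| | GM | Geometric CV% |
|---|---|---|
| No BLQ value | 50.0 | 79 |
| One value set to 0 (SAP rule) | 0 | undefined |

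With the zero in place, the arithmetic mean is 62.2, the arithmetic CV 75% and the median 50.0. The failure is confined to the geometric statistics.

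**2. How often a cell would contain a BLQ value.** The documents give no BLQ rates, so the rate p per sample is assumed. The probability of at least one BLQ value among n is 1 − (1 − p)^n.

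| Assumed p | n = 10 | n = 20 |
|---|---|---|
| 1% | 10% | 18% |
| 2% | 18% | 33% |
| 5% | 40% | 64% |
| 10% | 65% | 88% |

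The 20 is the approximate size of the FMI III extensive-sampling group in Protocol 10.5.3. The 10 would apply to Cohort 3 without expansion, if PK is tabulated by cohort. SAP 2.7.4.4 tabulates by treatment, and SAP 2.1.1.1 defines treatment as formulation. An FMI IV cell could therefore pool Cohorts 2 and 3 (20 + 10 = 30, or 20 + 20 = 40 patients), which raises the probabilities.

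**3. Which cells are likely to be affected.**

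- *Day 1 pre-dose, Cycles 2 to 6.* The Protocol Table 7 footnote lists the sampling days: "Extensive PK group (Table 11): C1D1,2,15,16; and C2-6 D1". Table 11 has 8 + 1 + 8 + 1 + 5 = 23 scheduled samples, and 5 of them follow the off week. From the Day 21 dose to the next Day 1 is 8 × 24 = 192 h. At 7 h, the upper Day 1 half-life in Protocol 1.2.1.2.1, that is 192/7 ≈ 27 half-lives. At an assumed 24 h it is 8 half-lives, a 2^8 = 256-fold decline. The reported 3- to 8-fold accumulation suggests slower elimination at steady state, so BLQ values here are probable, not certain.
- *Metabolites.* Protocol 1.2.1.2.1 says: "In most patients, BHS697 and BQR917 were measurable at levels of ~5-50%, and <15% of parent exposure, respectively". If exposure ratios are read as concentration ratios (an assumption), a metabolite at 15% of parent is BLQ when the parent is below 1.0/0.15 = 6.7 ng/mL, and at 5% when it is below 1.0/0.05 = 20 ng/mL.
- *Cycle 1 Day 1 pre-dose.* These samples precede any drug and should all be BLQ. Protocol 10.5.3.2.1 and SAP 2.7.4.1 and 2.7.4.3 admit only samples with an adequately recorded prior dose. Read literally, that excludes these samples, so they are not counted here.

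**4. Comparing replacement rules.** Simulation of 100,000 cells with n = 20, LLOQ 1.0 ng/mL, and assumed GM 5 ng/mL and geometric CV about 93%. Entries are median GM (ng/mL) / median geometric CV%.

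| | All cells | Cells with at least one BLQ value |
|---|---|---|
| Uncensored | 5.0 / 91% | 4.6 / 103% |
| LLOQ/2 | 5.0 / 93% | 4.5 / 113% |
| BLQ excluded | 5.2 / 84% | 5.2 / 84% |

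Under these assumptions LLOQ/2 stays closer to the uncensored result than exclusion does.

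**The case against.** The strongest objection concerns frequency. Protocol 1.2.1.2.1 reports that plasma levels were often unquantifiable at 5 and 10 mg/day but reliably quantifiable from 20 mg/day. Treatment here starts at 125 mg, and the lowest level in the dose reduction table is 50 mg. This stands for the parent drug on dosing days, including the 24 h sample on Cycle 1 Day 2, where mixed cells may be rare. The statement does not say which time points it covers, so it does not settle the off-week samples or the metabolites. The same section does call BHS697 and BQR917 measurable in most patients, which leaves room for some BLQ values.

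A second objection is that the separate PK plan may already refine the rule. That limits what can be said about the eventual tables. It does not rescue a general principle that cannot be computed, and a PK plan with a different rule would contradict the SAP.

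A reader might infer that every PK summary fails, or that the formulation comparison is lost. The documents do not support that. Cmax or AUC is zero only if all contributing concentrations are BLQ, and PK parameters come from the Cycle 1 Day 1 and Day 15 profiles. Among the parameters, exposure is mainly through Ctrough.

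**Conclusion.** The sentence in SAP 2.7.4.1 is wrong as written, and the point is minor. That a cell with one BLQ value gets a geometric mean of 0 and an undefined geometric CV% is a mathematical fact and rests on no assumption. How many cells are affected cannot be determined from the documents; the probabilities above depend on assumed BLQ rates.

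The effect is confined to the geometric columns for concentrations and Ctrough. Cmax and AUC are largely unaffected, arithmetic summaries and medians remain computable, and ORR and its confidence interval are untouched. Nothing here bears on the efficacy conclusions.

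**What to change.** Replace the sentence in SAP 2.7.4.1 with a rule of this kind: values below the LLOQ enter arithmetic summaries as zero; for the geometric mean and geometric CV% they are set to LLOQ/2; each cell shows the number and percentage of BLQ values; geometric statistics are not reported when more than half of the values in a cell are BLQ.

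Three accompanying steps are needed:

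- Keep a BLQ flag in the data, because Protocol 7.2.3.2 reports these values as 0 ng/mL and they must remain identifiable.
- Record the change from Protocol 10.5.3.1 in SAP section 4, "CHANGE TO PROTOCOL SPECIFIED ANALYSES", which currently lists none.
- Use the same rule in the PK analysis plan.

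The cost is a few lines of text, a check of the flag, and an added display of BLQ counts; no new data are needed. The downside is that LLOQ/2 is an approximation. In the simulation it lowers the geometric mean slightly and raises the CV (4.5 and 113% against 4.6 and 103% in cells with a BLQ value). The distortion is larger when a single BLQ value lies far below the rest. In the GM 50 example, LLOQ/2 gives 42.6 and 184%, and exclusion gives 53.8 and 71%, against 50.0 and 79% with no BLQ value. Showing the BLQ count makes such cells visible.
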